6.2.4. Schedule of Events

Potential participants may self-complete an IRB-approved online pre-screening survey. Those eligible based on survey responses will meet with the study team & Principal Investigator for the screening and baseline visit. If the subject agrees to take part in the study, they must read and sign a consent form, which will include the Inclusion/Exclusion criteria, information on completing the study

diary electronically as well as the covered medical expenses by the clinical study (see 6.2.5).

Schedule of Events

	Pre-Screening Phase	Treatment Phase		Post-Treatment	Unscheduled	
		Visit 1	Visit 2	Visit 3	Visit 4	Unscheduled
Visit Type	Pre-Screening	Screening/ Baseline	Follow-Up	Follow-Up	End of Study	Unscheduled
Visit Location	(virtual)	(in clinic)	(virtual)	(virtual)	(virtual)	(in clinic)
Window	(-42 to Day 1)	Day 1	Days 5-9	Days 21-24	Days 30-37	N/A
Procedure						
Pre-Screening Survey	Х					
Informed Consent		Х				
Demographics		Х				
Medical History		Х				
Concomitant Medications		Х	Х	Х	Х	
Modified Fitzpatrick Skin Type		Х				
Limited Dermatological Exam		Х				Х
Eligibility Determination		Х				
Device Use/ Band Application4		Х				
Band Re-application(s)		X _e				
eDiary Training		Х				
eDiary/Photo Review		х	Х	X¹	X ²	
Adverse Events		Х	Х	Х	Х	Х
Surgical Excision						X ³

¹ if treated skin tag(s) has/have not fallen off by Visit 3, participant has option to have skin tag(s) removed at an Unscheduled Visit by calling the Investigator's office and making an appointment

² no eDiary entries for this visit; only photo(s) to be submitted by participant and reviewed by Investigator to confirm coordinator may exit participant from study. If Investigator has concerns about participant's D30 photo, participant will have an Unscheduled Visit for examination

³ optional: presented to subject in the event the skin tag was not removed by STR study device by D10

⁴ Participants will complete the initial eDiary and photo(s) upload at the Day 1, in-clinic visit.

⁵ Band -Repplication to be performed by PI or Sub-I as needed at the site in the event of the band falling off. Participants will be allowed 2 reapplications per skin tag throughout the course of the study.

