2.2. Purpose of Investigative Study

The aim of this study is to investigate the safety and effectiveness of a mechanical device to remove skin tags in adults. The device utilizes the ligation method by applying a silicone band around the base of a skin tag, therefore restricting the blood supply, which is vital to its growth and survival. Because this method does not include freezing or burning of tissue in or around the skin tag, it could be considered less invasive and less risky than other options.

A clinical validation study to demonstrate the safe and effective removal of skin tags will be completed under the direction of an investigator (dermatologist or other health care professional) led protocol. This study will assess the proportion of skin tags successfully removed within a 20-day period, and to evaluate associated safety outcomes. Adult (22 years and above) subjects fitting the inclusion/exclusion criteria will be recruited, given they have one or more skin tags consistent with device labeling. All subjects entering the clinical study will have the device applied by the healthcare professional and proceed through the study, recording their experience using an electronic clinical diary to collect data.

Since this device is to be sold over-the-counter, evaluation of the subject's self-selection and label comprehension abilities will be completed under a separate Human Factors and Usability study and is therefore not required in the scope of this clinical trial.

3

³ UC Davis Dermatology Online Journal

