Visit 3 (virtual)	 At Visit 3, the subject is to complete a remote visit where the following activities are performed: The subject and study team member will review the eDiary and photos to verify completion through day 2 0 Subject to report any signs of infection, irritation, and adverse events to study team member. Subject should also provide information in eDiary identifying these issues Ensure recording of successful removal of the skin tag via STR study device (if applicable) Study team member and subject to review after care instructions to be followed through Visit 4 If skin tag has not fallen off, study team member to discuss the following options with subject: If subject wants skin tag to be removed, study team member instructs them to call Investigator's office for an Unscheduled Visit to have skin tag removed by Investigator

If subject is not interested in skin tag removal by Investigator, study team member instructs them to follow directions provided on After Care Instructions on proper self-removal of the band around treated skin tag
 Study team member to remind subject that an in-clinic visit is always available upon request up to Visit 4 and to call with any

questions or concerns

Secondary clinical endpoints and data collected are defined as follows:

Secondary Outcomes	Time Frame	Description and Data Collected	
Discomfort, issues, or adverse events occurring during the study	Visit 2 (virtual)	 The subject is to complete a virtual visit where the following activities are performed: General observations, as described by the subject, of the skin tag site Review photos uploaded to eDiary and discuss any issues with irritation, infection, or other adverse events Study team to review any instances of premature band detachment, and to remind participant to schedule a rebanding visit if not already completed Study team member to record and report any safety-related issues regarding irritation or infection to Investigator Remind subject to continue daily recordings in eDiaryto remain in study Study team member to review AEs and Concomitant Medications at virtual visit Study team member to remind subject that an in-clinic visit is always available upon request and to call with any questions or concerns 	

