	Visit 3 (virtual)	The subject is to complete a virtual visit where the following activities are performed: • General observations, as described by the subject, of the skin tag site. • Review photos uploaded to eDiary and discuss any issues with irritation, infection, or other adverse events • If skin tag(s) has/have not been removed by STR study device, study team member to review options with subject for tag removal. • If subject wants skin tag to be removed, study team member instructs them to call Investigator's office for an Unscheduled Visit to have skin tag removed by Investigator • If subject is not interested in skin tag removal by Investigator, study team member instructs them to follow directions provided on After Care Instructions on proper self-removal of the band around treated skin tag • Study team member to review AEs and Concomitant Medications at virtual visit • Study team member and subject to review After Care Instructions that are to be followed until Visit 4 (and beyond if	

	necessary). Study team member to remind subject that an in-clinic visit is always available upon request, up to Visit 4, and to call with any questions or concerns
Visit 4 (virtual)	The subject is to complete a remote visit where the following activities are performed: • Photo submission(s) of skin tag site(s) approximately 30 days (but not earlier than Day 30) after band(s) was/were placed • Investigator will review photo(s) and verify the subject is either cleared to exit study or needs to return to clinic for an Unscheduled Visit • Study team member to review AEs and Concomitant Medications at virtual visit once subject is cleared to exit study by Investigator

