6.2.6.1. Reported Post Study Data

Case Report Forms will be used by the CRO to collect and organize data. All data collected during the investigational study will be compiled by the CRO and securely stored by the Sponsor. Data collected will be captured and archived using a per-protocol approach.

The following table provides a list of the reported primary outcomes, as evidenced by the study. Data subgroup analysis following the completion of the study and performance data analysis reported by:

- Age (22-50 vs. 51+)
- Sex assigned at birth (M/F)
- Band size (micro vs. standard)
- Band detachment events, including duration of detachment
- Body location of band placement
- Mechanism of device used (automatic vs. manual)

Data Collected	Description
Proper band placement	Source: Visit 1, Investigator Records STR study device bands will be placed on up to two (2) skin tag(s) by the Investigator. Source: eDiary Participant will upload a photo(s) of the banded skin tag(s) in the eDiary at the Visit 1 in-clinic visit.

Efficacy of skin tag removal	Source: Days 2-2 O, Case Report Forms and Subject eDiary The total number of skin tags treated and those successfully removed by use of the STR study device will be compiled and reported. In all cases, the removal rate will be categorized by skin tag size (micro or standard) and body location as well as subject demographics
Safety and Potential Health Impacts	Source: Case Report Forms and Subject eDiary There are not any serious adverse effects anticipated with this study potential non-serious side effects during the use of the STR study device are as follows and will be collected: Irritation Tenderness Pigment change Scarring Less common but potential side effects that need to be collected and addressed are: Infection Redness or swelling at the base of tag Bleeding Pain Delayed healing (greater than 14 days after tag falling off/removal) Hypertrophic or Keloid scarring Other (as defined/described in the eDiary manual) General use comments by the subjects, including photos depicting the progression of the skin tag(s) treatment and after the tag has fallen of Only adverse events associated with the device will be recorded and documented as Adverse Device Effects (ADEs).

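### Footnote 3 of the Schedule of Events allows excision of a tag not removed by Day 10, while the removal outcome runs to Day 20 and the rest of the schedule places the option at Visit 3 (Days 21-24)

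*Protocol*

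**What the plan says.** The Surgical Excision row of the Schedule of Events (Protocol Section 6.2.4) is marked only in the Unscheduled column, which has no visit window. Its footnote 3 makes the procedure optional, to be "presented to subject in the event the skin tag was not removed by STR study device by D10".

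Three other current statements give a different time:

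- Footnote 1 of the same table: "if treated skin tag(s) has/have not fallen off by Visit 3, participant has option to have skin tag(s) removed at an Unscheduled Visit". Visit 3 is set at Days 21-24.
- Section 6.2.6, primary outcome, Visit 3 row: "If skin tag has not fallen off, study team member to discuss the following options with subject".
- Section 6.2.6, secondary outcomes, Visit 3 row: "If skin tag(s) has/have not been removed by STR study device, study team member to review options with subject for tag removal".

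On the outcome, Section 2.2 states: "This study will assess the proportion of skin tags successfully removed within a 20-day period". Section 6.2.1 has the diary completed every evening through Day 20, and Section 6.2.6.1 draws efficacy data from the same period. Section 6.2.6.1 also states: "The total number of skin tags treated and those successfully removed by use of the STR study device will be compiled and reported".

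Section 6.2.5 covers the cost of excision when the device has been unsuccessful and gives no day.

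**The concern.** At Day 10 the device has not yet failed by the protocol's own outcome definition, since ten days of the window remain. Footnote 3 would nevertheless allow excision to be presented then. Excision is irreversible: once the tag is cut off, nobody can learn whether it would have dropped by Day 20. No later analysis rule restores that observation, so this is an operational matter for the protocol itself.

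The summary of changes explains that the diary was extended to 20 days because tags may fall off after Day 10. Those late-dropping tags are the ones footnote 3 exposes. The same summary shows that Version 1 diaries ended at Day 10 and Visit 3 fell on Days 11-14, so the Day 10 cut-off looks like a leftover. That is an inference. The finding rests on the conflict within the current text, not on a difference from the superseded version.

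**Working it through.** **Timing of the excision offer**

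Inputs: excision cut-off Day 10 (6.2.4, footnote 3); outcome window to Day 20 (2.2); Visit 2 on Days 5-9 and Visit 3 on Days 21-24 (6.2.4).

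- Outcome window still open after the cut-off: 20 − 10 = 10 days (Days 11-20).
- Gap from the cut-off to the earliest Visit 3: 21 − 10 = 11 days.
- Scheduled visits between Day 9 and Day 21: none. An early excision would need an on-request clinic visit, which Section 6.2.6 says is always available. A rebanding visit is a less likely occasion, because Section 6.2.3 directs reapplication there.

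**Effect on the success rate**

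Inputs: 60% expected removal and 200 tags (6.1), so 0.60 × 200 = 120 removed. Assumption: an early-excised tag stays among the treated tags and is not counted as removed by the device. This is the natural reading of Section 6.2.6.1.

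- One tag that would have dropped by Day 20: 119/200 = 59.5%, a change of −0.5 points.
- One tag that would not have dropped: 120/200 = 60.0%, no change.
- In general, for k tags that would have dropped: (120 − k)/200.

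The documents give no value for k. For illustration only, k = 2 gives 118/200 = 59.0%, k = 5 gives 115/200 = 57.5%, and k = 10 gives 110/200 = 55.0%. For scale, the normal-approximation 95% half-width at 60% of 200, treating tags as independent, is 1.96 × √(0.6 × 0.4/200) = 6.8 points.

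**Remark: elapsed time at Visit 4**

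Inputs: Visit 4 on Days 30-37, timed from banding (6.2.4 and 6.2.6); prolonged healing means more than 14 days after fall-off or Investigator removal (9.2). For tag loss on day r and Visit 4 on day v, the visit lies beyond the threshold only if v − r > 14.

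- Earliest Visit 4, v = 30: 30 − 15 = 15 qualifies and 30 − 16 = 14 does not. A visit beyond the threshold is certain only for r ≤ 15.
- Latest Visit 4, v = 37: 37 − 22 = 15 qualifies and 37 − 23 = 14 does not. For r = 16 to 22 it depends on the visit day; for r ≥ 23 no day in the window is late enough.
- Fall-off on Day 20: 30 − 20 = 10 to 37 − 20 = 17 days of follow-up; the first day beyond the threshold is 20 + 15 = Day 35.
- Excision on Day 24: 30 − 24 = 6 to 37 − 24 = 13 days.

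**The case against.** The strongest reply is that the working procedures already point to Visit 3. The only contacts at which staff are told to discuss removal options are the Visit 3 rows. The Visit 2 row offers no excision and tells participants to continue the diary through Day 20 whether or not the tag remains. Covered excision is tied to device failure. An early excision therefore needs an on-request visit and a site that follows footnote 3 over footnote 1 and both endpoint tables. This stands, and it makes the exposure narrow. It does not remove the conflict: footnote 3 is attached to the excision row itself, and a site acting on it would be within the written protocol.

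Some stronger readings are not supported:

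- *Day 10 is the only timing condition on the procedure, or every other passage says Visit 3.* Footnote 1 also conditions removal at an Unscheduled Visit, so the schedule holds two conflicting conditions. Section 6.2.5 gives no day.
- *Early-excised tags would be dropped from the analysis, which could raise the rate.* A reader might infer this from "Data collected will be captured and archived using a per-protocol approach". That sentence concerns data capture and archiving and does not define an analysis set. How an early excision is scored may properly be left to the SAP.
- *Visit 4 assures detection of prolonged healing for losses through Day 15, and makes it impossible from Day 23.* The arithmetic measures elapsed time, not detection. A site that healed slowly but closed before Day 30 would look healed in the photo. A site still open can lead the Investigator to recall the participant, and the Unscheduled visit has no closing date and collects adverse events. The point is also unrelated to the Day 10 error, so it stands only as a remark.

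**Conclusion.** Footnote 3 is wrong as written and should be corrected. It conflicts with footnote 1, with both Visit 3 rows and with the 20-day outcome, and it permits an irreversible act on Days 11-20 while the primary outcome is open. The size is 0.5 percentage points for each affected tag, at 120 of 200 and on the assumption that the tag would have fallen off by Day 20 and is counted as not removed. The number of such tags is unknown, and nothing in the protocol suggests it would be large. No claim is made about the total bias.

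The Visit 4 timing is a minor follow-up observation: a visit beyond the 14-day healing threshold is certain for tag loss through Day 15, depends on the visit day for Days 16-22, and is not possible within the window from Day 23.

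**What to change.** In Section 6.2.4, footnote 3, replace the Day 10 condition with *by Visit 3 (after Day 20)*, so that it matches footnote 1. This changes a few words in one footnote and alters no visit, procedure or sample size.

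Optional, for the remark: where possible, take the virtual exit photo within the existing Days 30-37 window and at least 15 days after tag loss, for example Day 35 for a Day 20 fall-off. This fits the present window for losses through Day 22 (22 + 15 = 37) and needs no added visit. Later losses, chiefly excisions after Visit 3, would still rely on the Investigator's exit review and recall.

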6.2.5. Medical Expenses and Clinic Visits

Certain medical expenses will be covered during the study by the Sponsor. These include the following:

- investigational device costs
- clinical care costs for the placement and follow-up of the investigational device
- clinical care costs to remove skin tag in the event of failed treatment by device
 - o removal of skin tag via surgical excision if STR device unsuccessful
- up to 2 on site rebanding visits in instances of premature band detachment
- clinical care costs relating to the following adverse event when using the device:
 - o infection of the skin tag site

The following medical expenses will NOT be covered;

- cosmetic treatment related to pigment change or minor scarring at the skin tag site
- treatment related to hypertrophic scarring and/or keloids (subjects with these prior to consenting are excluded from study participation)

The study subjects will have access to a healthcare professional at the Investigator's clinic, including a 24-hour number to contact the investigator. If at any time the subject is concerned about treatment complications, they shall contact the PI immediately. An unscheduled visit may be performed.

6.2.6. Clinical Endpoints

Primary clinical endpoints and data collected are defined as follows:

Primary Outcome	Time Frame	Description and Data Collected
Successful removal of acrochordons using the STR device	Visit 1: subject screening and band placement (in-clinic)	 Obtain subject's informed consent Study team member to verify inclusion/exclusion criteria Identification of skin tag(s) to be used in study, including size (micro or standard) and location Documentation of body location and number of tags Investigator to stratify subject into either manual or automatic device arm Placement of band(s) by Investigator Placement of bandage(s) by investigator Subject to read after-care instructions & review any questions with study team Subject will receive clinical eDiary instructions comprising of device use, comprehension, and adverse events and later complete Day 1 entry Subject will upload a photo of the banded skin tag(s) in clinic

	 during Visit 1, which will be reviewed by the site staff Study team member to remind subject that an in-clinic visit is always available upon request and to call with any questions or concerns Study team member to remind subject to schedule an in-clinic rebanding visit at their earliest convenience in the event of premature band detachment
Visit 2 (virtual)	At Visit 2, the subject is to complete a remote visit where the following activities are performed: • Subject and study team member will review the photos and verify eDiary compliance for all days up to Visit 2 and also identify any signs of infection, irritation, or other adverse events • Study team member to record general observations of tag(s) treated, flagging any concerns to Investigator • Study team to review any instances of premature band detachment, and to remind participant to schedule a rebanding visit if not already completed • Subject to continue filling out eDiary through Day 2 oregardless if skin tag(s) remain(s) • Study team member to review after care instructions that are to be followed through Visit 4 • Study team member to remind subject that an in-person visit is always available upon request and to call with any questions or concerns
Visit 3 (virtual)	 At Visit 3, the subject is to complete a remote visit where the following activities are performed: The subject and study team member will review the eDiary and photos to verify completion through day 2 0 Subject to report any signs of infection, irritation, and adverse events to study team member. Subject should also provide information in eDiary identifying these issues Ensure recording of successful removal of the skin tag via STR study device (if applicable) Study team member and subject to review after care instructions to be followed through Visit 4 If skin tag has not fallen off, study team member to discuss the following options with subject: If subject wants skin tag to be removed, study team member instructs them to call Investigator's office for an Unscheduled Visit to have skin tag removed by Investigator

If subject is not interested in skin tag removal by Investigator, study team member instructs them to follow directions provided on After Care Instructions on proper self-removal of the band around treated skin tag
 Study team member to remind subject that an in-clinic visit is always available upon request up to Visit 4 and to call with any

questions or concerns

Secondary clinical endpoints and data collected are defined as follows:

Secondary Outcomes	Time Frame	Description and Data Collected	
Discomfort, issues, or adverse events occurring during the study	Visit 2 (virtual)	 The subject is to complete a virtual visit where the following activities are performed: General observations, as described by the subject, of the skin tag site Review photos uploaded to eDiary and discuss any issues with irritation, infection, or other adverse events Study team to review any instances of premature band detachment, and to remind participant to schedule a rebanding visit if not already completed Study team member to record and report any safety-related issues regarding irritation or infection to Investigator Remind subject to continue daily recordings in eDiaryto remain in study Study team member to review AEs and Concomitant Medications at virtual visit Study team member to remind subject that an in-clinic visit is always available upon request and to call with any questions or concerns 	
	Visit 3 (virtual)	The subject is to complete a virtual visit where the following activities are performed: • General observations, as described by the subject, of the skin tag site. • Review photos uploaded to eDiary and discuss any issues with irritation, infection, or other adverse events • If skin tag(s) has/have not been removed by STR study device, study team member to review options with subject for tag removal. • If subject wants skin tag to be removed, study team member instructs them to call Investigator's office for an Unscheduled Visit to have skin tag removed by Investigator • If subject is not interested in skin tag removal by Investigator, study team member instructs them to follow directions provided on After Care Instructions on proper self-removal of the band around treated skin tag • Study team member to review AEs and Concomitant Medications at virtual visit • Study team member and subject to review After Care Instructions that are to be followed until Visit 4 (and beyond if	

	necessary). Study team member to remind subject that an in-clinic visit is always available upon request, up to Visit 4, and to call with any questions or concerns
Visit 4 (virtual)	The subject is to complete a remote visit where the following activities are performed: • Photo submission(s) of skin tag site(s) approximately 30 days (but not earlier than Day 30) after band(s) was/were placed • Investigator will review photo(s) and verify the subject is either cleared to exit study or needs to return to clinic for an Unscheduled Visit • Study team member to review AEs and Concomitant Medications at virtual visit once subject is cleared to exit study by Investigator

